3.2.2 Potential Benefits

The treatment the participant receives may prove to be more effective than other available treatments. In addition, participant participation will aid researchers in evaluating new methods of how varenicline, a medication approved for combustible smoking, affects e-cigarette use behavior. Participants will also be compensated for their time.

4 Study Objectives

4.1 Hypothesis

We hypothesize that participants who receive varenicline will have higher rates of e-cigarette cessation

4.2 Primary Objective

The primary objective of this study is to determine whether varenicline increases cessation in e-cigarette users.

5 Study Design

5.1 General Design Description

For this preliminary, proof-of-concept study, we require smartphone ownership or email access to allow for receipt of weekly surveys (via text or email) during the sampling period, as well as weekly assessments (methods described below). According to the latest Pew survey, 77% of Americans own a smartphone; >73% among those under age 65. Requirement for smartphone ownership will not affect internal validity, but it could reduce external validity.²

This is a randomized, placebo-controlled, double blind pilot study. This study aims to enroll 20 adults who report daily mono- e-cigarette use at MUSC and 20 adults who report daily mono- e-cigarette use at Yale (N=40 total). This is a 12-week study with 8 weeks of study drug use (either varenicline or placebo) provided to the enrolled participants.

Inclusion/exclusion criteria will be determined via initial online screening and then confirmed with tele-video/phone call final screening. Non-pregnancy verification will be ascertained via remote pregnancy test. If any of these exclusions are endorsed, then the potential participant will not be enrolled into the study. Once screening and informed consent are complete, eligible participants will be randomized to 1 of the following 2 groups:

- 1) VRN + Self-Change Pamphlet
- 2) Placebo + Self-Change Pamphlet

All participants will be asked to provide assessments (as described below) throughout the sampling process to assess vaping & smoking behavior (if the participant initiates smoking after enrolling in the trial), craving, varenicline/placebo use, use of web-based program, etc.

Randomization: 20 participants per site (MUSC and Yale) will be stratified status of former or never smoker. Former smoker is defined as an individual who has smoked at least 100 cigarettes in their lifetime but have not smoked in the past 6 months or longer.

Study Details

Guided Self-Change Booklet: This 3-page pamphlet includes information on how to reduce and quit e-cigarettes on their own (on Page 1), how to prevent relapse to combustible cigarettes (for mono vapers who quit combustible cigarettes by vaping; on Page 2), and how to enroll in the online This is Quitting services (described above; on Page 3).

All groups will receive this pamphlet as a brief behavioral component of the intervention. This 2-page pamphlet will include information on how to reduce and quit e-cigarettes on their own on one page, how to prevent relapse to combustible cigarettes (for mono vapers who quit combustible cigarettes by vaping) on the second page, and the third page will contain information about how to enroll in the Truth Initiative/Mayo “This is Quitting” online self-guided e-cigarette treatment program (described below).

Truth Initiative/Mayo “This is Quitting” Program: All participants will be given information about how to enroll in treatment with the This is Quitting Program, which is a free online program that was created by the Truth Initiative in conjunction with Mayo Clinic as a tobacco cessation treatment tool. This program offers online and texting services that assist individuals with their quit attempts for general tobacco use, but they also have specific content/support for vaping. Upon enrolling in the program, the participant is prompted to select a quit date and give their contact

information (i.e., email and phone number). The participant is then granted access to the platform that gives them links with cessation tips such as how to deal with cravings, building a support system, dealing with relapse, using medication to help with cessation, etc. The This is Quitting Program also incorporates a text message option. This text message will send the participant 3-4 tobacco cessation related messages per day. If the participant texts "ECIG," a new text thread will be created that will send vaping related messages directly to the participant.

Pharmacotherapy: Twenty participants will be randomized to receive active varenicline. Prior to randomization, the study physician, [name] or nurse practitioners from the Tobacco Treatment Service/PI [name] will conduct a pre-randomization medical review to ensure that they qualify for varenicline based on study eligibility criteria collected during primary (e.g., smoking history, age, medical history, and comorbidities) and secondary screening (psychiatric history, suicidal history, pregnancy status). A summary report that we create within our REDCap screening database, will be delivered electronically to study physician/nurse practitioners/PI [name]. They will review each participant's information and will determine whether to 1) accept the individual into the study, 2) reject the individual into the study (i.e., not eligible for varenicline), or 3) ascertain more information from the individual before either the decision to accept/reject the participant. The study physician/nurse practitioners may contact the individual to engage in further clinical interviewing of the potential participant. The disposition of each participant will be tracked within this screening database, allowing us to complete all CONSORT steps to study flow. The individual will not proceed to randomization and intake until we have signed, explicit documentation from the study physician/nurse practitioners/ PI [name] to do so. Thus, these procedures ensure that we retain physician/APRN oversight and approval of varenicline disbursement at the study outset. [name]/APRNs from the Tobacco Treatment Service retains their role in evaluation of adverse events as noted elsewhere within this application.

Other contraindications for varenicline include suicidal ideation.²¹ Suicidality will be assessed at prior to randomization and during the follow-up assessments. If an individual endorses suicidality during the pre-randomization screening, they will be marked as ineligible for the study. This will be assessed using the PHQ9 toolkit for suicide ideation (refer to assessments section). An alert is programmed into the REDCap system that if an individual indicates an active plan to either physically harm or kill themselves, an alert will be sent to the study team. They will then be contacted by our clinical team to complete a risk assessment over via phone. A member of the clinical team will query the participant for details regarding the suicidal ideation, including a likelihood of harming oneself imminently and a plan for committing suicide. If the participant reports an imminent likelihood of harming him/herself or a plan for committing suicide, the clinical team member will call emergency services and will remain on the phone with the participant until emergency services arrive. In the event that the participant expresses an imminent likelihood of harming him/herself, and the connection is lost, emergency services will be contacted to provide emergency services with the participant's contact information, including address. If the participant is not in imminent danger, the clinical staff will provide referrals for local mental health resources and/or instruction to go to the ED or call 911 should suicidal ideation worsen. The clinical team member will suggest that the participant seek treatment and then will follow-up with the participant via phone one week later.

In the event that a participant endorses suicidal ideation but is not responsive to clinical staff's phone call within 48 hours, the participant will be emailed a list of local

mental health resources and will suggest that the participant seek additional treatment. The email will also ask that the participant respond to the clinical staff either via phone or e-mail within 24 hours to confirm receipt of the treatment referrals. Should the participant not respond to the clinical staff's email within an additional 48 hours (4 days from completion of the assessment)

We will utilize the PHQ9 assessment to track depression and suicidal ideation during the baseline assessments. If suicidal ideation is endorsed, an automated "red flag" will be processed through our REDCap database. This red flag will indicate either a a) clinically significant increase in total PHQ scoring with an overall score of at least 15 (>5 point increase from baseline and resulting score >15), OR b) any value >0 for item 9/suicidal ideation). The red flag indicators will be monitored daily by our clinical team and will be met with the appropriate measures. These measures are based on prior MUSC-IRB approved protocols of varenicline (i.e., the STARS Pro00098479).

We will work with the Investigational Drug Service (IDS) pharmacy (MUSC) and Yale-New Haven Pharmacy (Yale) to package and label varenicline. Both packaging and labelling will be done within the YNNH pharmacy, following all applicable laws. Under no circumstances will non-credentialed study staff package or label the medication. The IDS pharmacy (MUSC) and Yale-New Haven Pharmacy (Yale) will package and label the varenicline under our prescriber's order.

Upon receipt of medication, the participant will receive a call from our team. This will be a brief orientation call during which they will have an overview of the medication. All participants will be encouraged to start their medication as soon as they receive it and to set a quit date 1-2 weeks from medication initiation. The varenicline prescription will follow the standard induction period: varenicline 0.5 mg once per day for Days 1-3, varenicline 0.5 mg twice per day for Days 4-7, then varenicline 1 mg twice per day (when varenicline reaches peak efficacy for tobacco cessation). Participants will remain on varenicline for 8 weeks total. Dose adjustments (e.g., reduction to 0.5 mg twice per day if 1 mg is not well tolerated) will be allowed at the discretion of the clinical pharmacist/APRN/physician. An 8-week supply of varenicline will be shipped.

A novel alert system will be built into the Adverse Event surveys REDCap database such that any severe adverse events (e.g., severe nausea, severe sleep disturbances, severe changes in mood) that are endorsed along with self-report of cessation of pharmacotherapy use will be monitored by research staff, who will consult with the study physician/APRN from the Tobacco Treatment Service/PI [name] when indicated for clinical assessment and management. We believe this alert system will improve varenicline medication adherence if the pharmacist/APRN/physician can quickly follow-up on any side effects that may be associated with pharmacotherapy use and call the patient with any recommended dose adjustments. All dose adjustments will be recorded in our REDCap database.

Guided Self-Change Pamphlet: All groups will receive this pamphlet as a brief behavioral component of the intervention. This 3-page pamphlet includes information on how to reduce and quit e-cigarettes on their own (on Page 1), how to prevent relapse to combustible cigarettes (for mono vapers who quit combustible cigarettes by vaping; on Page 2), and how to enroll in the online This is Quitting services (described above; on Page 3).

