6.1.3 Dosage, Administration, Schedule

Dose and schedule: We are using the same dose of the oral medication for vapers as we would for cigarette smokers. The participants will be given a dose titrated to 2mg daily which aligns with the current FDA approved dose for smoking cessation. The varenicline prescription will follow the standard induction period: varenicline 0.5 mg once per day for Days 1-3, varenicline 0.5 mg twice per day for Days 4-7, then varenicline 1 mg twice per day (when varenicline reaches peak efficacy for tobacco cessation). Participants will remain on varenicline for 8 weeks total. Dose adjustments (e.g., reduction to 0.5 mg twice per day if 1 mg is not well tolerated) will be allowed at the discretion of the clinical pharmacist/APRN/physician. The entire 8-week supply of varenicline will be shipped at week 1 according to the Pharmacy's workflow..

Medication Schedule: Both groups will follow the same medication schedule (listed below).

- Days 1-3: 0.5mg (or matching placebo) study pill once per day
- Days 4-7: 0.5mg (or matching placebo) study pill twice per day
- Weeks 2-8: 1mg or matching placebo) study pill twice per day

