Weekly Electronic Assessments: Participants will be asked to complete a brief compensated assessment to assess e-cigarette use, use of other tobacco products including cigarettes, and daily medication adherence. These Assessments be completed weekly throughout the entirety of the study. Assessments will assess vaping sessions/puffs per day, use of other tobacco products, medications/products used, purposes of that use (to reduce/quit), next-

day e-cigarette use/other tobacco use/quit intentions, and mood/affect. The assessment will also assess e-cigarette brand, concentration, and habits surrounding e-cigarette use (i.e., location, type of device, and flavor choice). Weekly abstinence will be assessed in three different ways: "Have you quit today?", "Have you used an e-cigarette in the past three days?", and "Have you used an e-cigarette in the past 7 days?" To track medication adherence, the assessment will also ask how many varenicline pills that participant took per day. This will not replace traditional adverse event assessment (below) but complement (and enrich) them. We have established procedures to auto-send an email or SMS text (their choice) on a set schedule. SMS text messaging is possible via Twilio, embedded within our REDCap system, which allows participants to complete a survey directly from their phone, without having to access a webpage. Note that assessments are not completed via texting, just prompted via text with link to REDCap. Participants can choose to receive their assessment invitations via email if they wish, again with a link to a secure REDCap survey. Thus, per eligibility criteria above, we require participants to have smartphone or other device that has internet capacity. Assessments consist of a brief (<2 minutes) survey, directly enter an online protected database (REDCap) through secure encryption; all PHI is protected. Participants will be compensated for compliance based on % assessments completed (described below).

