6.2.3 Adverse Events Definition and Reporting

Adverse Events:

Participants will have the phone numbers of the Co-PIs, [name] [contact]) and [name] [contact]) and will be prompted to contact them if an adverse event occurs, along with the previously mentioned adverse event procedures. If a participant contacts the research team due to an adverse event, the event will be appropriately addressed, and the event will be reported per the criteria below. Adverse events will also be tracked via weekly assessments, where they will be able to rate the incident as mild, moderate, or severe. The research staff, with the guidance of [name] (for MUSC) and [name] (for Yale), will track the relatedness of the incident to study medication. The variables that we will encourage the pharmacist/APRN to assess include severe renal impairment, history of serious hypersensitivity or skin reactions to varenicline, an immediate (within 2 weeks) post myocardial infarction period, serious arrhythmias, unstable angina pectoris, or hemodynamically or electrical instability. We will determine if any adverse events result in dropouts or are serious according to FDA guidelines.

Serious adverse events, whether unanticipated or anticipated, will be reported immediately (within 24 hours) to the MUSC or Yale Institutional Review Board. The PIs will evaluate the adverse event and determine whether the adverse event affects the Risk/Benefit ratio of the study and whether modifications to the protocol or the consent procedures are required.

Plans for reviewing and reporting non-serious anticipated or unanticipated adverse events: Any participants' experiences of anticipated and unanticipated adverse events will be reported on an annual basis to the MUSC Institutional Review Board.

Plan for grading adverse events. Serious Adverse Events (SAE). The FDA's definition of serious adverse events (21 CFR 312) will be used. Serious Adverse Events include any untoward medical occurrence that at any dose results in death or the immediate risk of death, hospitalization, or the prolonging of an existing hospitalization, persistent or significant disability/incapacity or a congenital anomaly/birth defect, new cancer, or medication overdose. Adverse events will be defined and graded for risk as follows:

Coding of Severity:

- 0 = No adverse event or within normal limits
- 1 = Mild adverse event
- 2 = Moderate adverse event
- 3 = Severe, resulting in psychiatric or medical hospitalization

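### As worded, the adverse event alert requires a severe event plus self-reported stopping of study drug, so a severe event in a participant still taking capsules triggers no automated adverse event alert

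*Combined protocol and SAP*

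**What the plan says.** The alert is described once, in the pharmacotherapy part of Section 5.1 (General Design Description). It is built into the REDCap adverse event surveys. It concerns severe events, with nausea, sleep disturbance and mood change as the examples, "that are endorsed along with self-report of cessation of pharmacotherapy use will be monitored by research staff". Staff then consult the study physician, APRN or PI "when indicated for clinical assessment and management".

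The next sentence gives the purpose: "We believe this alert system will improve varenicline medication adherence if the pharmacist/APRN/physician can quickly follow-up on any side effects" and can call the participant with a recommended change of dose. The same section sets out the change: "Dose adjustments (e.g., reduction to 0.5 mg twice per day if 1 mg is not well tolerated) will be allowed at the discretion". That decision rests with a pharmacist, APRN or physician.

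Section 6.2.3 supplies the severity information: "Adverse events will also be tracked via weekly assessments, where they will be able to rate the incident as mild, moderate, or severe". Section 6.2.1 supplies the drug-taking information: "To track medication adherence, the assessment will also ask how many varenicline pills that participant took per day". It adds of the weekly survey: "This will not replace traditional adverse event assessment (below) but complement (and enrich) them".

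**The concern.** The alert exists so that a clinician can step in early and keep the participant on drug. The tool for this, a reduction to 0.5 mg twice daily, is most useful to someone who is tolerating the capsules poorly but still taking them. A trigger that waits for stopping leaves that person out and fires only once adherence has already failed.

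The setting adds some weight. Section 6.3.1 says the trial is run entirely remotely. After the orientation call, the schedule in Section 6.3.5 lists only weekly assessments, a drug shipment and the exit survey. Staff will therefore learn of poor tolerability largely from what participants enter in surveys or choose to report by phone. At stake are the speed of clinician follow-up and the chance of a timely dose reduction.

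**Working it through.** No arithmetic applies, and the plan gives no figure to reproduce. The check has three steps.

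**1. Trigger logic.** There are two inputs: whether the participant rates an event severe, and whether the participant reports having stopped study drug.

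| Event rated severe | Drug stopped | Alert as worded | Alert after the fix |
|---|---|---|---|
| Yes | Yes | Yes | Yes |
| Yes | No | No | Yes |
| No | Yes | No | Yes, if the stop is attributed to an adverse event |
| No | No | No | No |

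The second row is the gap. The third is a smaller one: a participant who stops because of an event rated moderate is also not flagged by this system.

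**2. Any other automated trigger.** The other automated clinical flags are psychiatric:
- The suicide-plan alert (Sections 3.2.1, 5.1, 6.1.3 and 7.12) fires on a stated plan.
- The PHQ-9 red flag (same sections) fires on any positive answer to item 9, or on a rise of more than 5 points to a total above 15.

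Neither depends on stopping drug, so either may catch a severe mood change. Neither responds to an event rated severe as such. Severe nausea and severe sleep disturbance, two of the alert's three examples, have no automated backstop. The compliance prompt in Section 6.1.3 is a text to participants whose assessments show non-compliance. It responds to missed capsules, not to severity.

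**3. Non-automated routes.**
- Weekly severity ratings are tracked by research staff, with a lead at each site who guides the judgement of relatedness (Section 6.2.3).
- Participants are prompted to phone the Co-PIs if an event occurs (Section 6.2.3).
- A weekly meeting reviews the status of all enrolled participants and any adverse events (Section 7.11).
- Dose reduction is at clinician discretion and does not depend on the alert (Sections 5.1 and 6.1.3).

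A severe event on treatment is therefore recorded and reviewed by people. What is missing is the automated prompt. If surveys are completed and meetings held as planned, the weekly meeting bounds the wait for that review at about a week after the survey entry.

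**The case against.** The strongest reply is that the phrase is ambiguous. It could mean that severe events and self-reported stopping are each monitored, and the stated aim of following up side effects generally fits that meaning better. The REDCap build is not in the documents, so a reader who infers that the alert will in fact miss these participants goes further than the text allows. This stands as a limit on the point. It does not remove it, because the conjunctive reading is the natural one and this sentence is the only specification of the alert. If either condition was meant to suffice, the rewording simply makes that plain.

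A second reply is that someone who has stopped can be called and may resume at a lower dose, so the alert as worded still serves adherence. That is fair. The alert is narrower than its aim, not useless.

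Three stronger readings are tempting and not supported:
- **That severe events on treatment go undetected.** The weekly ratings, prompted calls and weekly review say otherwise.
- **That leaving self-rated severe, non-serious events out of the 24-hour report is a second gap.** That report is for serious events, and leaving non-serious ones out is correct routing.
- **That the gap can be sized by the active arm or by the days at full dose.** Section 6.1.3 sets "Weeks 2-8: 1mg or matching placebo) study pill twice per day", but the alert wording does not depend on dose. Under the blind it covers both arms on every dosing day.

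**Conclusion.** The point holds as a minor one. As worded, any of the 40 participants who rates an event severe while still taking capsules raises no automated adverse event alert, and this fits poorly with the alert's own purpose. The consequence is slower clinician follow-up and possible delay in a dose reduction, not missed detection.

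Its size cannot be put as a number of participants, because the documents give no severe-event rate and none is assumed here. Nor can the time saved be stated exactly: the plan sets no response time for the alert, and clinician consultation is a staff judgement even when it fires.

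The conclusion rests on the conjunctive reading of one sentence and on the alert being programmed as that sentence is written. Outcomes, analysis and sample size are unaffected.

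**What to change.** Reword the alert sentence in Section 5.1, and set the REDCap logic to match, so that research staff are alerted and consult the study physician or APRN for:
- (a) any event the participant rates severe, whether or not study drug was stopped; and
- (b) any self-reported stop that the participant attributes to an adverse event.

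The clinical action, including any dose change, stays with the study clinician.

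The cost is one sentence, one logic edit and, if the surveys do not already ask it, one item on the reason for stopping (the weekly assessment as described asks for pill counts). The downside is a few extra alerts for staff to review among 40 participants.
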